2. To define the effects of targeted and the combination of immune and molecularly targeted therapy on tumor microenvironment

[figure not shown]
Study Design:

A Simon 2-stage design will be implemented for each disease cohort. Patients will be treated with two-week lead-in of molecularly targeted therapy (MTT), followed by two 3 week cycles of combined targeted therapy (MTT) and pembrolizumab (at dose of 200 mg IV every three weeks), followed by maintenance single-agent pembrolizumab in all patients with RECIST defined stable disease (SD), partial response (PR), and complete response (CR). MTT *only will be resumed* if patients develop symptomatic or radiographic evidence of progression. If patients do not develop evidence of progressive disease (PD), then they will continue maintenance single-agent pembrolizumab for up to two years. In each cohort, patients will be accrued to first stage of the Simon design. If a prespecified number of patients maintain SD/PR/CR off MTT but on pembrolizumab at the 24-week time point, then the second stage of the two-stage design will be opened. (Please see details in statistical section) Biopsies will be performed on all patients enrolled to the first stage of the Simon two-stage for each cohort. These will be obtained at baseline and after the two-week lead-in. A third biopsy obtained after the completion of induction therapy will be obtained if feasible. An optional biopsy at time of disease progression will also be performed.

CONFIDENTIAL

This document is confidential. Do not disclose or use except as authorized.

SCHEMA

WT = wild-type; MT = mutant

Key Eligibility:

- Participants must have histologically confirmed metastatic or unresectable melanoma.
- Participants must have BRAFV600-mutation status known.
- Participants must have measurable disease.
- Age greater than or equal to 18 years.
- Participants must have disease amenable to and be willing to undergo serial core or excisional biopsies of a tumor lesion(s).
- ECOG performance status ≤ 1 (see Appendix A).
- Participants must have normal organ and marrow function as defined below:
- Participants not previously treated with BRAF inhibitors (vemurafenib, dabrafenib, encorafenib), MEK inhibitors (selumetinib, trametinib, binimetinib, cobimetinib), and/or anti-PD1/PDL1 monoclonal antibodies for metastatic or unresectable disease. Any other prior therapy *will be* allowed (including ipilimumab, adjuvant anti-PD1 therapy, high-dose IL-2).

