This trial has two planned cohorts, BRAFV600 mutant (cohort 1) and BRAF-wild-type melanoma (cohort 2). Treatment commences with 2 weeks of MTT (dabrafenib plus trametinib in cohort 1, trametinib in cohort 2), then two 3 weeks cycles of concomitant MTT and pembrolizumab, followed by single-agent pembrolizumab thereafter. Serial biopsies will be performed prior to MTT, and (if feasible) following the 2-week lead-in of MTT, and (if feasible) following six weeks of combination immune therapy and MTT. An optional biopsy at time of disease progression will also be performed. This trial represents a unique opportunity to not only test the effectiveness of combined immune and MTT, but also to determine which patients are most likely to benefit from this approach and, more importantly, to begin to understand why patients do or do not benefit. This valuable information that may lead to the next wave of combinatorial therapy in melanoma that involves MTT, anti-PD1 therapy, and other agents that target critical mediators of adaptive or innate resistance to combined MTT and pembrolizumab. Due to a recent shortage of research grade dabrafenib and trametinib, we plan to use commercially availability dabrafenib and trametinib. Since we cannot guarantee supply of "off-label" trametinib for cohort 2, we will open cohort 1 initially and consider

CONFIDENTIAL

This document is confidential. Do not disclose or use except as authorized.

opening cohort 2 in mid-2017, after more data is available for MEK inhibitors in patients with BRAF wild-type melanoma.

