13.5 Analysis of Correlative Measures

Analysis of MTT induced changes on T-cell clonality / PDL1 expression and correlation with clinical benefit. To investigate whether MTT-associated changes following a brief course of MTT can predict who will benefit from the addition of anti-PD1 therapy, assessments will be based on: (a) clonality of tumor-infiltration lymphocytes (TILs), and (b) PD-L1 IHC. TIL clonality is a term used to quantify the diversity of clones and frequency of any given clone. It is calculated by ImmunoSeq Adaptive Biotechnologies software using a clonality score, defined as $[1 - (\text{entropy}) / \log_2(\# \text{ of productive unique sequences})]$, where the entropy term takes into account the varying clone frequencies of TILs. A maximally diverse population, where every sequence is represented one time, is associated with a clonality score of zero, and a perfectly monoclonal population with a clonality score of one. Assessment times will be pre-treatment and after the 2-week MTT lead-in. Each cohort will be investigated separately.

To investigate the hypothesis that there will be an increase in TIL clonality after MTT lead-in, the overall changes in clonality of TILs after MTT will be expressed as a fold-change (2-week/pre) and compared with unity using a Wilcoxon signed-rank test with 80% power, and a 0.1, two-sided significance level. For a range of standard deviations of the fold-change between 0.8 and 1.2, we will be able to detect effect sizes between 1.4 and 1.65 for this comparison. We will further refine this question to address whether increases in clonality are related to response. Clones that comprise the largest percentage of the total T-cell population after MTT lead-in will be identified and sorted by frequency. The percentage of the overall T-cell population included in the top 5% of clones will

be compared according to response (achieving/not achieving clinical benefit) using Wilcoxon rank-sum tests. If the observed CBR is 0.75, resulting in 19 patients with clinical benefit and 6 without, a Wilcoxon rank-sum test with 0.1, two-sided significance level will have 80% power to detect a difference in percentage T-cells that is approximately 1.3 times the common standard deviation. Similar analyses will be performed for the top 2.5% or 1% of clones.

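### Testing the raw clonality ratio against 1 tilts the signed-rank test towards a false increase, and the 80% power claim gives no number of biopsy pairs

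*Combined protocol and SAP*

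**What the plan says.** Section 13.5 states the aim in these words: "To investigate the hypothesis that there will be an increase in TIL clonality after MTT lead-in". The change in each patient is "expressed as a fold-change (2-week/pre) and compared with unity using a Wilcoxon signed-rank test", at 80% power and a two-sided 0.10 level, separately in each cohort. No log transform is mentioned.

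The power statement reads "For a range of standard deviations of the fold-change between 0.8 and 1.2", then "we will be able to detect effect sizes between 1.4 and 1.65 for this comparison". It gives no number of pairs and does not say whether 1.4 and 1.65 are means or medians. The next comparison in the same section, a rank-sum test, does give group sizes: "If the observed CBR is 0.75, resulting in 19 patients with clinical benefit and 6 without", 25 in all.

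The documents differ on who provides a pair of biopsies:

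- The synopsis and sections 1.1, 2.4 and 5.1 name patients in the first Simon stage (14 evaluable per cohort, section 13.1) and are silent on the second stage.
- Section 9.1 requires biopsies in all patients, but on the premise that all are in the first stage. That conflicts with the 14 + 11 design.
- Inclusion criterion 3.1.8 and study calendar footnote k carry no stage limit.
- On the two-week sample, section 2.3 says "Serial biopsies will be performed prior to MTT, and (if feasible) following the 2-week lead-in of MTT". The synopsis and section 1.1 say "These will be obtained at baseline and after the two-week lead-in" and attach the feasibility condition only to the third biopsy.

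**The concern.** The one-sample signed-rank test ranks distances from the null value and assumes that equal distances either side are equally likely. If the lead-in does nothing, a patient's two clonality scores are exchangeable. The log of their ratio is then symmetric about 0, but the ratio itself is not symmetric about 1. The resulting bias points the same way as the trial's hypothesis.

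The effect of therapy on the tumour microenvironment is a secondary objective, and immunoSEQ is one of the two assays that sections 2.4 and 9.1 name for a predictive model. A test that leans towards the hoped-for result weakens that conclusion. Separately, a power claim with no sample size cannot be compared with the number of pairs the trial will actually have.

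**Working it through.** **1. The plan's own figure.** Inputs from section 13.5: SD 0.8 with fold 1.4 (shift 0.40); SD 1.2 with fold 1.65 (shift 0.65); two-sided 0.10; power 0.80. By the normal approximation, n = ((1.645 + 0.842) × SD / shift)²:

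- SD 0.8: (2.487 × 2.000)² = 24.7
- SD 1.2: (2.487 × 1.846)² = 21.1

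Simulating the signed-rank test with exact critical values and normal shifts, 25 pairs reach 80% power at folds of about 1.42 and 1.64. Power at exactly 1.4 and 1.65 is 0.76 and 0.82. The claim therefore fits about 25 complete pairs, although no single number fits both ends exactly.

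**2. Can the ratio be symmetric about 1?** A non-negative ratio symmetric about 1 lies between 0 and 2. Its SD is largest, at 1.0, with half the values at 0 and half at 2. If it is single-peaked, the limit is the uniform distribution, 2/√12 = 0.58. SDs of 0.8 to 1.2, if they apply under no change, do not fit a symmetric single-peaked ratio.

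**3. Size of the tilt.** Assume log-normal ratios with median 1 and log-SD s, so SD² = e^(s²)(e^(s²) − 1). SD 0.8 gives e^(s²) = (1 + √3.56)/2 = 1.443 and s = 0.606. SD 1.2 gives (1 + √6.76)/2 = 1.8 and s = 0.767. Simulated rejection rates with no true change (intended: 0.05 for an increase, 0.10 two-sided) are:

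| Ratio SD under no change | 25 pairs: increase | 25 pairs: two-sided | 14 pairs: increase | 14 pairs: two-sided |
|---|---|---|---|---|
| 0.3 | 0.09 | 0.11 | 0.07 | 0.10 |
| 0.5 | 0.11 | 0.13 | 0.08 | 0.11 |
| 0.8 | 0.14 | 0.16 | 0.10 | 0.12 |
| 1.2 | 0.17 | 0.18 | 0.11 | 0.13 |
| Log ratio, any SD | 0.05 | 0.10 | 0.05 | 0.09 |

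The log-ratio errors split evenly by direction. The exact attained two-sided levels are 0.096 at 25 pairs and 0.091 at 14.

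The result does not depend on log-normality. With both scores drawn independently from the same beta distribution (four shapes tried), the raw ratio gives a false increase in 0.17 to 0.23 of cohorts at 25 pairs. The log ratio and the simple difference stay at 0.045 to 0.049 per side.

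**4. If the SDs belong to the effect and not to the null.** Reading 1.4 and 1.65 as means, s² = ln(1 + (0.8/1.4)²) = 0.283 and ln(1 + (1.2/1.65)²) = 0.425, so s = 0.532 and 0.652. The two-sided error is then 0.144 to 0.164 at 25 pairs and 0.112 to 0.122 at 14.

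**5. Power if fewer pairs exist** (normal-shift reading, at the stated effects; 20 and 11 pairs assume about 20% of two-week samples are not obtained):

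| Pairs | Power | Folds detectable with 80% power |
|---|---|---|
| 25 | 0.76–0.82 | 1.42–1.64 |
| 20 | 0.67–0.73 | 1.48–1.71 |
| 14 | 0.52–0.57 | 1.59–1.88 |
| 11 | 0.41–0.46 | 1.69–2.03 |

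The rank-sum claim of 1.3 SD has power 0.82 at 19 v 6, but 0.58 at 10 v 4 and 0.53 at 11 v 3.

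Fourteen is a realistic number even if everyone is biopsied. P(X ≤ 8 of 14) is 0.788 at a clinical benefit rate of 0.50 (the plan gives 0.79) and 0.112 at 0.75.

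**6. Log-normal reading of the stated effects** (SD 0.8 to 1.2 held at the effect). As means, power at 25 pairs is 0.73–0.85 raw and 0.53–0.67 log; at 14 pairs it is 0.48–0.60 raw and 0.34–0.43 log. As medians, 14 pairs still give 0.86–0.96 raw and 0.77–0.91 log.

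**The case against.** - **The number of pairs can be inferred.** Section 13.2 gives 25 per cohort, section 13.5 uses 19 + 6, and 25 pairs come close to the stated effects. This is right: the power figures are not arithmetically wrong. What remains is that 25 is unstated and that the biopsy passages do not secure it.
- **The largest error rates assume the SDs hold under no change.** The plan does not say so. If they are SDs at the effect and 1.4 to 1.65 are medians, the two-sided error at 25 pairs is about 0.136 to 0.150. The range is lower, but a false increase still occurs in about 12% to 13.5% of cohorts. The size depends on the reading; the direction does not.
- **A shortfall at 14 pairs is not certain.** On the median reading there is none. This stands, and is a reason to state which is meant.
- **The biopsy conflict is milder than it looks.** Sections 2.4 and 9.1 make tissue collection subject to safety, the feasibility clause in 5.1 may cover the two-week sample, and 14 counts evaluable patients, not pairs. But the synopsis and 1.1 tie feasibility to the third biopsy only, and the safety clause concerns collecting tissue at a time-point, not whether the two-week biopsy is required.
- **A paired difference would also hold its level and needs no zero rule.** True, but it abandons the fold-change the plan chose to report.
- **The work is mostly exploratory and no trial decision rests on this p-value.** This stands and limits the weight of the point.

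**Conclusion.** The concern holds. As written, the clonality test is biased towards the hypothesised increase. Under log-normal ratios with the plan's SDs taken at the null, the chance of a false increase is 0.14 to 0.17 at 25 pairs and 0.10 to 0.11 at 14, against 0.05. At a null SD of 0.3 it is still 0.09 at 25 pairs. The direction follows from exchangeability alone; the size rests on the assumed distribution and on where the SDs apply.

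The power claim is broadly consistent with 25 complete pairs, but that number is neither stated nor assured. On the normal-shift reading, power at 14 pairs is 0.52 to 0.57. The point should be corrected, but it touches a correlative analysis only.

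**What to change.** **Test.** In section 13.5, apply the signed-rank test to log2(2-week/pre) against 0. Add a rule for zero scores, which the section's own definition allows: "A maximally diverse population, where every sequence is represented one time, is associated with a clonality score of zero". Rank a zero at either time as the most extreme value in its direction, and treat 0/0 as no change. State the effect detectable with 80% power in SDs of the log ratio: 0.53 for 25 pairs, 0.60 for 20, 0.73 for 14 and 0.86 for 11. If median folds are quoted, name the SD convention:

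| Ratio SD 0.8–1.2 taken | 25 pairs | 14 pairs |
|---|---|---|
| At the effect | 1.31–1.40 | 1.42–1.55 |
| Under no change | 1.38–1.50 | 1.56–1.76 |

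**Pairs.** Reconcile the synopsis, sections 1.1, 2.3, 2.4, 5.1 and 9.1, criterion 3.1.8 and calendar footnote k on whether second-stage patients are biopsied and whether the two-week biopsy is required. In 13.5, state the number of complete pairs assumed and whether 1.4 to 1.65 are means or medians.

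- If biopsies stop at the first stage, restate the detectable effects for 14 pairs: about 1.59–1.88 fold on the normal-shift scale, and for the rank-sum tests about 1.73 SD (10 v 4) or 1.87 SD (11 v 3).
- If all 25 are biopsied, the present normal-shift figures can serve for 25 pairs. Add the 14-pair figures for a cohort that stops early, and allow for missing two-week samples (20 pairs: about 1.48–1.71 fold).

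**Cost.** Wording only, with no new samples. The price is apparent power: if 1.4 to 1.65 are log-normal means, power at 25 pairs falls from 0.73–0.85 to 0.53–0.67, and the log test reaches 80% at mean folds of about 1.48–1.71. Part of what is lost was the bias itself.

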2.3 Rationale

It has been shown that inhibition of the mitogen-activated protein kinase (MAPK) pathway in patients with melanoma, through inhibition of BRAF and/or MEK, leads to increased melanoma antigen expression, decreased immunosuppressive cytokines, increased trafficking of CD8+ T-lymphocytes, and upregulation of immune exhaustion markers such as PD1 and PDL1. Also, in collaboration with Adaptive Biotechnologies, we have shown that patients with a higher proportion of preexisting tumor infiltrating lymphocyte clones, determined by T-Cell Receptor (TCR) rearrangement sequencing (so-called ImmunoSeq), have better outcomes with BRAF/MEKi therapy, although nearly all patients have an increase in TCR clonality in the setting of BRAF/MEKi therapy. The major conclusion from this data is that MAPK pathway targeting enhances anti-tumor immunity within the tumor microenvironment, which provides a strong rationale for combination MAPK targeted therapy with immune targeted therapy.

A number of trials of combination MAPK targeted therapy (MTT) with immune targeted therapy have been opened in recent years with mixed results. One of the major issues has been tolerability, particularly with combinations of MTT and ipilimumab. We believe that the value of combining MTT with immunotherapies, such as pembrolizumab, is that MTT may enhance immune responses in the tumor microenvironment and convert an immunologically non-responsive tumor microenvironment into an environment that is responsive to anti-PD1 immunotherapy. Thus, we are interested in testing trial designs that incorporate a lead-in phase of MTT and a brief period of concomitant MTT and immune targeted therapy.

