To assess if changes in clonality after MTT lead-in are associated with infiltration by new TIL clones, we will compare pre-treatment and post-MTT biopsies to identify clones that were absent from the pre-treatment biopsies, and summarize the percentage of individual clones that were identified to be new. This will be assessed for all patients in a cohort using Wilcoxon signed-rank tests, and according to clinical response using Wilcoxon rank-sum tests. In additional analyses, the percentage of pre-existing clones, rather than new clones, will be compared according to response to see if patients with high proportions of pre-existing clones after MTT lead-in exhibit a better response than patients with low proportions.

For PD-L1 expression, patients will be classified, retrospectively, into two subgroups defined by clinical benefit at 24 weeks. Fold-changes in PD-L1 IHC (2-week/pre) will be compared for patients achieving/not achieving clinical benefit using Wilcoxon rank-sum tests. If the observed CBR is 0.75, resulting in group sizes of 19 and 6, a Wilcoxon rank-sum test with 0.1, two-sided significance level will have 80% power to detect a difference in fold-changes that is approximately 1.3 times the common standard deviation.

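### Section 13.5 asks whether increases in clonality relate to response, but its test uses only the post-lead-in top-clone share and cannot separate an MTT-associated increase from a difference present before treatment

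*Combined protocol and SAP*

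**What the plan says.** Section 13.5 opens its clonality and PD-L1 analyses with the aim "To investigate whether MTT-associated changes following a brief course of MTT can predict who will benefit from the addition of anti-PD1 therapy". Assessments are at pre-treatment and after the 2-week lead-in, separately by cohort.

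Three steps matter here:

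- **Overall change.** The clonality fold-change (2-week/pre) is tested against 1 by a signed-rank test in the whole cohort.
- **Relation to response.** The plan continues: "We will further refine this question to address whether increases in clonality are related to response". The step that follows works from the week-2 biopsy alone: "Clones that comprise the largest percentage of the total T-cell population after MTT lead-in will be identified and sorted by frequency". The variable tested is how much of the T-cell population the top 5% of those clones hold, and a rank-sum test sets patients with benefit against those without. The same is done for the top 2.5% or 1%. Power is given thus: "If the observed CBR is 0.75, resulting in 19 patients with clinical benefit and 6 without", a two-sided 0.10 rank-sum test has 80% power for a difference of about 1.3 common SDs in the percentage.
- **PD-L1.** "Fold-changes in PD-L1 IHC (2-week/pre) will be compared for patients achieving/not achieving clinical benefit using Wilcoxon rank-sum tests".

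Section 13.5 also compares by response the percentages of clones that are new, or were already present, relative to the pre-treatment biopsy. Section 2.3 reports that "patients with a higher proportion of preexisting tumor infiltrating lymphocyte clones" had better outcomes on BRAF/MEK inhibitor therapy.

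**The concern.** The question is about an increase, which needs two time points per patient. The variable tested has one. A tumor already dominated by a few clones that did not change during the lead-in can score the same as one that became dominated because of it.

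No other listed analysis fills the gap. The fold-change test is not split by benefit. The new-clone and pre-existing-clone percentages use both biopsies, but they measure clone turnover: a tumor can become more clonal without gaining new clones, or gain many new clones without becoming more clonal. For PD-L1 the section does compare the change by benefit, so the clonality analysis is out of step with its companion.

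At stake is the interpretation of the result. A significant difference could be read as lead-in therapy expanding clones in the patients who go on to benefit, when the data would be equally compatible with a baseline association. A baseline difference in the other direction could hide a real effect of change. Sections 2.4 and 9.1 name immunoSEQ as one of two assays to enter a predictive model, so the reading matters beyond one table.

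**Working it through.** **1. The plan's own figure.** Inputs from section 13.5: 19 vs 6 patients, two-sided alpha 0.10, difference 1.3 SD, stated power 80%. The noncentral t calculation with the minimum rank-test efficiency of 0.864 gives 80.1%. Simulating the exact rank-sum test on normal data gives 81.9%, with actual size about 9% because the test is discrete. The figure reproduces, but it is power for a difference in week-2 level.

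**2. Assumptions for the check (not in the documents).** Pre-treatment values are normal with SD 1. The benefit group starts d SD higher. MTT has no effect that differs by benefit. The pre/post correlation ρ is 0.5 to 0.85. Three models for the week-2 value:

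- A: pre-treatment value plus independent noise, so the week-2 SD rises to 1/ρ.
- B: week-2 SD stays at 1 and the full gap d persists.
- C: week-2 value = ρ × pre-treatment value + noise, SD 1, so values regress toward a common mean.

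**3. The gap each test sees, in SDs of the variable tested.**

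- Post-only: ρd in A and C; d in B.
- Change (week 2 minus pre): 0 in A and B. In C the mean gap is −(1−ρ)d and the SD of the change is √(2(1−ρ)), so the gap is −d√((1−ρ)/2).

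Examples at d = 1.3: post-only under A with ρ = 0.5 sees 0.5 × 1.3 = 0.65 SD; under B it sees 1.3 SD. The change under C sees −1.3 × √0.25 = −0.65 SD at ρ = 0.5, and −1.3 × √0.075 = −0.36 SD at ρ = 0.85.

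**4. Simulated chance of significance** (19 vs 6, exact rank-sum, two-sided 0.10; simulation error under about one percentage point; ranges are over ρ and, for the post-only column, over models):

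| Baseline gap d | Post-only (planned) | Change, models A and B | Change, model C |
|---|---|---|---|
| 0 | about 9% | about 9–10% | about 9–10% |
| 0.5 SD | about 13–25% | about 9–10% | about 11–14% |
| 1.0 SD | about 25–63% | about 9–10% | about 14–25% |
| 1.3 SD | about 35–82% | about 9–10% | about 17–35% |

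The low post-only ends come from A or C at ρ = 0.5; the high ends come from B. Under B, a pure baseline gap of 1.3 SD is declared significant about as often (81–82%) as a true MTT-related gap of that size.

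**5. Power cost of using the change.** For a true differential shift of 1.3 SD at week 2 and no baseline gap, the gap in SDs of the change is 1.3/√(2(1−ρ)):

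| ρ | Gap in SDs of change | Power, change | Power, post-only |
|---|---|---|---|
| 0.3 | 1.10 | about 69% | about 82% |
| 0.5 | 1.30 | about 82% | about 82% |
| 0.7 | 1.68 | about 95% | about 81% |
| 0.9 | 2.91 | nearly 100% | about 82% |

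**The case against.** The strongest case for the plan has four parts.

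- **It is not blind to baseline.** The new-clone and pre-existing-clone comparisons by response use the pre-treatment biopsy and help show whether clones seen after the lead-in were there before. Sections 2.4 and 9.1 also commit in general terms to relating longitudinal changes to outcome. This stands as partial context. It does not supply a comparison of the change in clonality by benefit.
- **The evidence for a baseline difference is indirect.** A reader might infer from section 2.3 that an imbalance between benefit groups is to be expected. The text does not go that far. It concerns pre-existing clones, not top-clone share, and outcome on BRAF/MEK inhibitors, not 24-week benefit off MTT on pembrolizumab. A baseline difference is plausible; its size and direction are unknown.
- **Misreporting is not prescribed.** A reader might also infer that a baseline difference will be reported as an MTT-induced predictor. Nothing in the plan says how the result will be worded, and most of the correlative work is called exploratory. What the text supports is that the two explanations cannot be told apart from this test.
- **A change score is not a full cure.** This stands. If values regress toward a common mean, the change test also rejects too often, with the group that started higher showing the smaller increase. A baseline-adjusted comparison and display of both time points are needed beside it.

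**Conclusion.** The mismatch between question and test is plain in section 13.5 and is not repaired elsewhere in the document. As written, the plan can show that patients with a dominant-clone repertoire after the lead-in do better or worse; it cannot show that an increase in clonality is related to response.

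How often this would mislead depends on a baseline gap that the documents do not quantify. Over assumed gaps of 0.5 to 1.3 SD, the planned test is significant in about 13% to 82% of trials with no differential MTT effect, against about 9% with no gap. These figures rest on normal data, the plan's 19 vs 6 split, and correlations of 0.5 to 0.85.

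The point is limited to this correlative analysis. The whole-cohort fold-change test is correctly matched to its own question, and the Simon decision on clinical benefit is unaffected. It should be corrected because the remedy is cheap and the plan already uses the change form for PD-L1.

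**What to change.** Amend section 13.5 as follows:

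1. Make the by-benefit test a rank-sum comparison of the within-patient change (2-week vs pre-treatment) in the clonality score and in the top 5%, 2.5% and 1% shares.
2. Add, as a check, a baseline-adjusted comparison of the 2-week value, for example a rank-based regression on benefit group and the pre-treatment value.
3. Show pre-treatment and 2-week values by benefit group. If the post-only comparison is kept, label it an on-treatment association rather than an MTT effect.
4. Restate the 1.3 SD detectable difference in SDs of the change, with the assumed pre/post correlation.

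The cost is wording: both biopsies and the assay are already in the plan. Patients without a usable biopsy pair drop out of this comparison, as they already do for the PD-L1 fold-change. Power is lower than for the post-only test if the pre/post correlation is below about 0.5 (about 69% against 82% at a correlation of 0.3), and higher above that.
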